Consent. Patients completed an electronic consent form in REDCap and pre-treatment questionnaires during the first study visit. Participants were deemed eligible based on the screening questions they completed on the REDCap online screen & phone screen. Patients also completed pre-treatment measures at this consent visit: Demographic Data Survey, PSFS, PROMIS-anxiety, PROMIS-depression, PROMIS-Physical Function (PF) and the Credibility and Expectancy Questionnaire (CEQ: Devilly & Borkovec, 2000). We also included the Cognitive Flexibility Scale (Martin & Rubin, 1995, CFS), Brief Experiential Avoidance Questionnaire (Gamez, et.al, 2013, BEAQ), and Southampton Mindfulness Questionnaire (Chadwick, et al., 2008, SMQ) at intake and the 1-week post-treatment to explore changes from pre- to post-intervention. Participants who attended this first remote visit were then mailed an Accusplit Pedometer to begin using 1 week before their first therapy session, to track the number of daily steps. They were emailed an electronic Word document of a weekly table for tracking steps. For those in Phase 2, they were mailed the pedometer as well as a measuring tape and electrical tape.

Phase 1. The purpose of Phase 1 was to adapt self-guided and therapist-delivered versions of the UP from the existing UP-5 using stakeholder feedback. We also examined physical function and physical activity as independent variables that may serve as moderators and as outcomes. We used a successive cohort design and delivered the UP-5 to two cohorts of two patients. Treatment was provided via telehealth by the Roybal Center interventionist, who has expertise delivering evidence-based psychological therapies to older adults. All sessions were audio or video recorded to be rated for therapist adherence. Patients were asked for consent to record.

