PSFS scores were analyzed using mixed effects linear growth models with time, treatment condition, and their interaction as predictors(Curran et al., 2010). Random effects modeled variation in intercepts, slopes over time, and their covariance. Time was specified as a continuous variable, centered on the date of the final observation, and scaled so that 1-unit represented the median duration between the first treatment session and the 1-month follow-up visit (10.5 weeks). The SG group served as the reference level for the treatment factor. Models were estimated in a Bayesian framework using default priors in the *brms* package(Bürkner, 2017). Four Markov Chain Monte Carlo chains were run with a warmup period of 1,000 iterations and a total of 4,000 iterations per chain, resulting in a posterior distribution of 12,000 candidate models. Convergence was assessed using the potential scale reduction factor (Rhat), with values close to 1 indicating good performance. Density plots of predictions from 100 random draws of the posterior distribution were overlayed against the empirical distribution of the response variable to visually inspect how well our model captured underlying patterns in the data.

To identify the optimal functional form of change over time, we compared nested unconditional models with different specifications of the time trend using leave-one-out cross-validation(Vehtari et al., 2017). Given only three observations per participant, we limited our

comparisons of temporal trends to a simple linear growth model and a piecewise growth model with two linear segments joined by a knot at the 1-week follow-up visit. The model with higher expected log pointwise predictive density (ELPD) indicated greater fit to the data. The number of highly influential observations (i.e., Pareto k values > 0.7) was also taken into consideration to assess the reliability of the predictive accuracy estimate. If the difference in ELPD was trivial compared to the standard error of the difference, or the number of influential observations was considerably larger in the piecewise trend, then the simple linear trend was retained for the final conditional growth model to evaluate treatment-by-time interactions.

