Additional clinical self-report outcomes (three PROMIS scales, BEAQ, CFS, and SMQ) were analyzed similarly to the primary endpoint using Bayesian mixed effects growth models with random intercepts, slopes, and their covariance. First, the optimal functional form of the temporal trend (i.e., linear or piecewise trajectory) was determined for each outcome variable by comparing nested unconditional models as previously described. Then, outcome variables with the same form of trajectory were simultaneously predicted in a multivariate mixed effects model, with level-1 residuals allowed to covary across outcomes, and separate (i.e., uncorrelated) blocks for level-2 random effects². For each outcome variable we assessed the existence of effects as well as the clinical significance of the between-treatment difference in change scores using the ROPE-full method, as defined by \pm 0.1* σ outcome baseline.

Secondary Endpoints – Physical Activity Measures

SPPB gait speed was analyzed in a two-way (treatment-by-time) mixed effects linear regression model with random intercepts, estimated via restricted maximum likelihood. The ANOVA-like specification was selected instead of the growth model as there were only two timepoints per participant.

In contrast, the large number of repeated observations for weekly average daily steps allowed for modeling potentially complex nonlinear trends. Step counts were analyzed using a multiple-group mixed effects model with a latent basis growth specification, estimated via maximum likelihood with the *nlme* package(Pinheiro et al., 2023). Initially, random effects for intercepts and total growth were included, but the model could not converge; thus, only random intercepts were retained. In the latent basis growth model, the optimal shape of the temporal trajectory is estimated directly from the data, similar to factor loadings in confirmatory factor analysis(Ram & Grimm, 2007). Two basis vectors, A_0 and A_1 , each with seven elements (corresponding to the number of measurement occasions per person), described the pattern of change over time separately within SG and TD groups. A_0 was a fixed vector of 1s, while A_1 contained two fixed elements for model identification – the first

² Across outcomes, we identified a single outlier value on the CFS that was non-credible (based on the subsequent and succeeding scores for that participant) and replaced that data point using multiple imputation.

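### The PSFS and self-report growth models leave the arms free to differ at baseline, so the arm comparison is unbiased but less precise than a baseline-adjusted one

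*SAP*

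**What the plan says.** The SAP (Primary Clinical Endpoint) fits PSFS with a mixed-effects growth model "with time, treatment condition, and their interaction as predictors". "Random effects modeled variation in intercepts, slopes over time, and their covariance". Time is continuous and "centered on the date of the final observation", and one unit is 10.5 weeks. The final model is used "to evaluate treatment-by-time interactions". The choice of time trend is restricted with the remark "Given only three observations per participant", so the pre-treatment score is one of the three outcome rows and not a covariate. Priors are the package defaults. Baseline PSFS otherwise appears only as an SD, which scales the ROPE (±0.1 baseline SD) and the standardized effects.

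Under Secondary Endpoints – Self-Report Forms, the three PROMIS scales, BEAQ, CFS and SMQ are "analyzed similarly to the primary endpoint using Bayesian mixed effects growth models".

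The protocol (Consent) places the baseline questionnaires before treatment: "Patients also completed pre-treatment measures at this consent visit: Demographic Data Survey, PSFS" and others. Under Phase 2 it says that patients were randomized through REDCap, with eight in each arm. It does not say whether randomization came before or after those questionnaires.

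**The concern.** With a treatment term and a treatment-by-time term, each arm has its own line. Time zero is the final visit, so the arm difference at Time = −1 is the treatment coefficient minus the interaction coefficient, and nothing restricts it. In effect, the arm comparison is a difference in raw change. If baseline was measured before allocation, any baseline difference between randomized arms is chance. The model nevertheless estimates that difference and passes part of it into the slope contrast.

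The protocol's secondary aim is to compare the self-guided and therapist-delivered versions. With 8 per arm, precision is the main limit on that comparison, and the SAP judges it against a narrow ROPE. The trial already holds a score that could make the comparison more precise.

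**Working it through.** **Inputs.** From the documents: 8 per arm, three PSFS observations per participant, ROPE half-width 0.1 baseline SD. Assumed, because the documents do not give them: r from 0.3 to 0.9, and equal variances across visits. Results are in baseline-SD units. The SAP gives no precision figure for the arm contrast, so there is none to reproduce. Its 80% power for an effect of .60 is attached to the pre/post models, without alpha or N, and is not used here.

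**1. Size of a chance imbalance.** SD of the baseline difference = √(2/8) = 0.50. Expected absolute difference = 0.50 × √(2/π) = 0.40.

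**2. How much reaches the contrast.** For change from baseline to the final visit, the expected shift given D is rD − D = −(1−r)D. In a three-visit linear model with visits at −1, −0.41 and 0 (assumed) and equal correlations, the slope weights are about −1.05, 0.12 and 0.93. The shift is then −1.05(1−r)D, nearly the same. Simulated two-visit trials gave regression slopes on D of −0.70, −0.50 and −0.30 at r = 0.3, 0.5 and 0.7, and about 0 after adjustment. The mean contrast was about 0, so there is no bias.

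| r | Expected absolute shift, (1−r) × 0.40 | Relative to ROPE half-width |
|---|---|---|
| 0.3 | 0.28 | 2.8 |
| 0.5 | 0.20 | 2.0 |
| 0.7 | 0.12 | 1.2 |
| 0.8 | 0.08 | 0.8 |

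**3. Precision if r were known.** Variance of the change contrast = 2(1−r) × 2/8. Variance of the baseline-adjusted contrast = (1−r²) × 2/8. The ratio is (1+r)/2. At r = 0.5 the SE is √0.25 = 0.500 against √0.1875 = 0.433. In the three-visit model with known covariance, the ratio of common-baseline to free-baseline variance is 0.58, 0.71, 0.83 and 0.89 at r = 0.3, 0.5, 0.7 and 0.8 with no slope variance. With a slope SD of 0.5 it is 0.64, 0.77, 0.88 and 0.93.

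**4. Precision when the adjustment is estimated.** With 16 participants, estimating the baseline slope multiplies the adjusted variance by 1 + 1/(16−4) = 13/12.

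| r | (1+r)/2 | × 13/12 | Two-visit simulation |
|---|---|---|---|
| 0.3 | 0.65 | 0.70 | 0.71 |
| 0.5 | 0.75 | 0.81 | 0.81 |
| 0.7 | 0.85 | 0.92 | 0.93 |
| 0.8 | 0.90 | 0.975 | 0.97 |
| 0.9 | 0.95 | 1.03 | 1.04 |

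Break-even is (1+r)/2 × 13/12 = 1, so r = 24/13 − 1 = 0.85. Above that, adjustment costs a little precision.

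**5. Effect on power.** Take a difference of 0.60 SD, r = 0.5, two-sided 0.05 and the normal approximation. Power is Φ(0.60/0.500 − 1.96) = 22% unadjusted and Φ(0.60/0.433 − 1.96) = 28% adjusted with r known.

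**The case against.** The specified model is a conventional growth model and is valid. A reader might infer from the free baseline that the treatment-by-time contrast is biased. It is not: averaged over randomizations it is centered on the true difference. The issue is efficiency, and sensitivity to the imbalance that happened to occur.

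A reader might also infer that any baseline difference must be chance because the questionnaires belong to the consent visit. The documents support pre-treatment but not pre-allocation. Participants know their arm once assigned, and these are self-reports, so the order matters. Mailing of the self-guided manual after consent fits baseline-first but does not prove it.

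A third tempting reading sets the raw expected imbalance of 0.40 SD against the ROPE and calls it four times the half-width. The ROPE applies to the treatment contrast, which moves by only (1−r) of the imbalance.

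Two further objections stand. The known-covariance ratios flatter the gain at this sample size. The practical change is also modest, since power for 0.60 SD stays at or below about 28% at r = 0.5. None of this removes the point that a baseline score already collected goes unused as an adjustment.

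**Conclusion.** The point holds as a loss of precision and a sensitivity to chance imbalance, for PSFS and the six self-report secondary outcomes. It is not an error that invalidates the reported analysis. Its size depends on r, which must be assumed. For r up to about 0.7 the expected shift exceeds the ROPE half-width and adjustment lowers the variance by at least 7–8%. At r = 0.8 both effects are small, and by 0.85–0.9 the precision gain is gone. Treating a baseline difference as chance also requires that the questionnaires were completed before randomization, which the documents leave open.

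**What to change.** 1. State whether the consent-visit questionnaires were completed before randomization.
2. If they were, add a baseline-adjusted analysis of PSFS, the three PROMIS scales, BEAQ, CFS and SMQ: model the 1-week and 1-month scores with the baseline score as a covariate.
3. An alternative is to re-origin time at each participant's consent-visit baseline, constrain the arms to a common mean there, and keep the treatment-by-time terms (both segments where the piecewise form is selected). This is not equivalent to step 2, because with a linear trend it makes the arm difference grow linearly from zero. If an effect appears by 1 week and then plateaus, the constrained linear contrast overstates the 1-month difference by about 11% at r = 0.5, against about 5% for the current model's contrast.
4. Do not simply delete the treatment term under the current centering, since that would force the arms to be equal at the final visit. Nor is Time = −1 a safe anchor: it lies 10.5 weeks before the 1-month follow-up, while treatment could start up to a month after consent.
5. The SAP heads this section as analyses completed after data collection. Present the result as a labeled sensitivity analysis beside the reported model, not as a replacement.
6. Leave gait speed and steps out, because those baselines may follow the mailing of arm-specific material.

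The cost is a small amount of re-analysis with no new data. The downside is little or no gain if r is high.

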Additional clinical self-report outcomes (three PROMIS scales, BEAQ, CFS, and SMQ) were analyzed similarly to the primary endpoint using Bayesian mixed effects growth models with random intercepts, slopes, and their covariance. First, the optimal functional form of the temporal trend (i.e., linear or piecewise trajectory) was determined for each outcome variable by comparing nested unconditional models as previously described. Then, outcome variables with the same form of trajectory were simultaneously predicted in a multivariate mixed effects model, with level-1 residuals allowed to covary across outcomes, and separate (i.e., uncorrelated) blocks for level-2 random effects². For each outcome variable we assessed the existence of effects as well as the clinical significance of the between-treatment difference in change scores using the ROPE-full method, as defined by \pm 0.1* σ outcome baseline.

Secondary Endpoints – Physical Activity Measures

SPPB gait speed was analyzed in a two-way (treatment-by-time) mixed effects linear regression model with random intercepts, estimated via restricted maximum likelihood. The ANOVA-like specification was selected instead of the growth model as there were only two timepoints per participant.

In contrast, the large number of repeated observations for weekly average daily steps allowed for modeling potentially complex nonlinear trends. Step counts were analyzed using a multiple-group mixed effects model with a latent basis growth specification, estimated via maximum likelihood with the *nlme* package(Pinheiro et al., 2023). Initially, random effects for intercepts and total growth were included, but the model could not converge; thus, only random intercepts were retained. In the latent basis growth model, the optimal shape of the temporal trajectory is estimated directly from the data, similar to factor loadings in confirmatory factor analysis(Ram & Grimm, 2007). Two basis vectors, A_0 and A_1 , each with seven elements (corresponding to the number of measurement occasions per person), described the pattern of change over time separately within SG and TD groups. A_0 was a fixed vector of 1s, while A_1 contained two fixed elements for model identification – the first

² Across outcomes, we identified a single outlier value on the CFS that was non-credible (based on the subsequent and succeeding scores for that participant) and replaced that data point using multiple imputation.

coefficient set to 0 and the last set to 1. The remaining five elements of A_1 were freely estimated, with each basis coefficient representing the proportion of total change occurring between the first and last measurement occasions. PerRam and Grimm (2009), the multiple-group growth model can be expressed as follows:

Avg Daily Steps[Visit]_n =
$$g_{0nc} * A_{0c}[Visit] + g_{1c} * A_{1c}[Visit] + e[Visit]_{nc}$$

The subscript c denotes the respective treatment group (SG or TD) for individual n, g_0 represents the expected starting value of weekly average daily steps, and g_1 represents the expected change in average daily steps from pre-treatment to 1-month follow-up .

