Those who did not consent to recording were still allowed to participate in the study. During each treatment session, participants reported the number of steps they took daily over the past week to the study interventionist. Starting at session 2, the interventionist completed a Clinical Global Impressions-Improvement (CGI-I) rating and documented how much homework the participant completed since the last session (0-100%). After the fifth session, participants were reminded to track their number of steps over the next week. One week later, patients provided feedback about the treatment in exit interviews. Interviews inquired about modifications needed to develop the self-guided UP-5 (e.g., automatic prompts) and whether/how to include a support person (e.g., caregiver) in treatment as well as treatment preferences and length of treatment. Patients also completed post-treatment measures at this 1-week f/u visit: PSFS, PROMIS-anxiety, PROMIS-depression, PROMIS-PF, CFS, BEAQ, SMQ, and the Credibility and Expectancy of Improvement Scale (CEIS). They also provided an electronic form for the interventionist to enter the number of steps they had taken over the past week. After each cohort, the UP-5 was adapted to reflect the stakeholder feedback, and the revised treatment was delivered to the subsequent cohort. At the end of Phase 1 we developed a self-guided version of the UP-5.

Phase 2. Phase 2 was a pilot randomized controlled trial comparing the adapted self-guided and therapist-delivered versions of the UP-5. As in Phase 1, participants completed the PROMIS_PF at both intake and post-treatment follow-up to assess physical function. Patients were randomized to complete one of these two treatments using the randomization module in REDCap. Each arm had eight patients. Therapist-delivered treatment was provided via telehealth. All sessions were audio or video recorded to be rated for therapist adherence. Patients were asked for consent to record. Those who did not consent to recording were still allowed to participate in the study.

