Adapting the Unified Protocol to Facilitate Activity in Older Adults

NCT04837521

Analytic Plan

Document Date: 2/25/2025

Analytic Plan:

For Aim 1 exit interviews will be analyzed using a rapid coding process designed to provide results quickly for healthcare providers. Coding will be conducted after each cohort and will inform revisions to the UP-5.

Aim 2. will be evaluated using descriptive statistics of treatment satisfaction, percent of sessions attended, retention rate, and therapist adherence. 80% retention and 80% therapist protocol adherence will be evidence of acceptability and feasibility. Change of 2.8 on mean PSFS score will be considered significant.

We will calculate differences pre- and post- intervention on measures of emotional distress and daily activity using general linear models. These calculations, which will include 95% confidence intervals, will provide information about the possible range of effect sizes and whether there is "signal" in improving these outcomes. Based on prior UP studies, we anticipate 80% power to detect at least a moderate effectsize of .60.

Analyses completed after data collection:

All analyses were conducted using R software.

Feasibility and Acceptability

Treatment feasibility was assessed via attrition and session attendance rates. We planned to compare attrition using a generalized linear model with a logit link function (McCullagh, 1984) and session attendance rates using a Z-test of two proportions. Within the TD group, descriptive statistics were also computed for participant homework completion and therapist adherence ratings to the protocol.

Treatment acceptability was assessed via CSQ total scores, and treatment recommendation ratings from the CEQ. CSQ scores were analyzed by a two-way (treatment-by-time) mixed effects linear regression model utilizing the *lme4* package(Bates et al., 2015). Random intercepts were included for participants, and the model was estimated using restricted maximum likelihood. Time was specified as a factor variable with levels for the 1-week and 1-month follow-up visits. Post-hoc contrasts evaluated the significance of differences in estimated marginal means between interventions at each timepoint. The recommendation ratings from the CEQ were analyzed in a two-way (treatment-by-time) mixed effects ordinal logistic regression model with random intercepts per participant, utilizing the *ordinal* package(Christensen, 2023).

Primary Clinical Endpoint

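### One CFS score was replaced after data collection with no prior rule and no described analysis of the observed score; with eight patients per arm the CFS contrast may depend on it, by an amount set by an unstated visit and displacement

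*SAP*

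**What the plan says.** The CFS is one of six secondary self-report outcomes in the SAP. Each is fitted with a Bayesian growth model. Outcomes that share a trend form (linear or piecewise) then enter one joint model, "with level-1 residuals allowed to covary across outcomes".

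Footnote 2 to that section says "we identified a single outlier value on the CFS that was non-credible". The ground given is "based on the subsequent and succeeding scores for that participant", and the analysts "replaced that data point using multiple imputation". All of this stands in the part of the SAP headed "Analyses completed after data collection". The forward-looking part of the SAP has no outlier or data-validity rule.

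The between-arm result is judged by the "clinical significance of the between-treatment difference in change scores using the ROPE-full method", with limits of plus or minus "0.1* σ outcome baseline". On sample size, Protocol Phase 2 says "Each arm had eight patients".

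The documents do not give the arm, the visit, the observed score, whether the judgement was blinded to arm, the imputation model, the number of imputations or the pooling. They mention no scoring error, out-of-range entry or source check. They describe no CFS analysis with the score kept or simply set to missing.

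**The concern.** Change in CFS over time is the quantity being estimated. A score was set aside because it disagreed with the participant's other CFS scores, so the criterion was the outcome trajectory itself, applied once the data were in hand. Such a criterion favours values that fit a smooth growth curve. If the score was genuine, replacing it also makes the residual scatter look smaller than it was.

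With eight patients per arm, one score can carry visible weight. The SAP's decision rule depends on both the location and the spread of the posterior: an effect must exist, and less than 5% of the posterior may lie in the ROPE. Replacing a discordant score can change both. A reader of the SAP cannot tell whether a CFS conclusion rests on this one decision.

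**Working it through.** The documents give no figure for the effect of the replacement, so there is nothing to reproduce. What can be computed is how far one score can move the contrast.

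**Inputs**
- Patients per arm: 8 (Protocol, Phase 2).
- Visits: baseline, 1 week and 1 month after treatment. One time unit is 10.5 weeks and the last visit is time 0 (SAP, Primary Clinical Endpoint). I place baseline at −1.
- The 1-month visit is about 5 weeks after the final session (Protocol, One month F/u), so the 1-week visit falls about 4 weeks before it: −4/10.5 = −0.38.
- ROPE: half-width 0.1 baseline SD, full width 0.2.
- Displacement k, the distance of the observed score from its replacement in baseline SD: **not stated, so an assumption**. I use k = 3 as the working value and show others.

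**Linear trend.** The estimated total change is the least-squares slope over one time unit. A visit at time t has weight w = (t − mean t) / Σ(t − mean t)². The mean time is −0.46, and the weights are −1.06, 0.16 and 0.90. One displaced score moves the arm contrast by abs(w) × k / 8.

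| Visit of the score | Weight | Shift | Shift at k = 3 | Half-widths | Full widths |
|---|---|---|---|---|---|
| Baseline | −1.06 | 0.132k | 0.40 SD | 4.0 | 2.0 |
| 1 week | 0.16 | 0.019k | 0.06 SD | 0.6 | 0.3 |
| 1 month | 0.90 | 0.113k | 0.34 SD | 3.4 | 1.7 |

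If the 1-week visit is put at −0.41, its weight is 0.12 and the shift at k = 3 is 0.12 × 3/8 = 0.045 SD. At −0.48 the shift is 0.01 SD.

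**Other values of k, baseline or 1-month score:** k = 2 gives 0.23–0.26 SD (1.1–1.3 full widths), k = 4 gives 0.45–0.53 SD (2.3–2.6), and k = 5 gives 0.57–0.66 SD (2.8–3.3). A shift of three full widths (0.6 SD) needs k between 0.6 × 8/1.06 ≈ 4.5 and 0.6 × 8/0.90 ≈ 5.3.

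**Piecewise trend, 1-week score.** The score sits at the knot. Each segment's change moves by k/8, which is 3/8 = 0.375 SD (1.9 full widths). The two movements have opposite signs, so total change moves by about 0.

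**Check by simulation.** In 60 simulated trials (8 per arm, random-slope mixed model, assumed variance components, 1-week visit at −0.41, one score moved 3 SD) the median shifts were 0.393 SD (baseline), 0.045 (1 week) and 0.349 (1 month). The standard error of the contrast rose from about 0.49 to 0.57–0.63 SD, so keeping the score also widens the posterior.

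**The ROPE can move too.** With 16 patients, a baseline score displaced by k inflates the baseline SD by about √(1 + k²/16), which is 1.25 at k = 3. The full ROPE width becomes 0.2 × 1.25 = 0.25, and the baseline shift is then 0.40/0.25 = 1.6 full widths.

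**Sensitivity to the time of baseline.** Questionnaires were completed at the consent visit, up to a month before treatment. If baseline is dated 4 weeks earlier, at −14.5/10.5 = −1.38, the weights become −0.78, 0.20 and 0.58. The shifts at k = 3 become 0.29, 0.08 and 0.22 SD.

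**The case against.** The strongest reply is that the visit decides the size, and on one plausible reading the size is negligible. Taken literally, the footnote compares the score only with later ones, which points to baseline. But its two adjectives mean the same thing, and one may be a slip for *preceding*. With three visits, only the 1-week score has a neighbour on each side. On that reading the effect on total change is about 0.05 SD or less at k = 3. This stands, and the documents cannot settle it. It does not remove the point entirely, because a discordant 1-week score could still affect the choice between linear and piecewise trends, and so which joint model CFS enters.

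A reader might infer that one score moves the contrast by four or five ROPE widths. The documents do not support that: those multiples are half-widths, and the displacement is unknown. Against the simulated standard error, the shift is also modest: 0.40/0.49 ≈ 0.8 standard errors for a baseline score and 0.05/0.49 ≈ 0.1 for a 1-week score. No changed CFS conclusion has been shown.

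A reader might also infer that the score was genuine, or that no analysis with it was ever run. Neither follows. It may have been a recording or response error, in which case keeping it would overstate the variance, and properly done multiple imputation carries uncertainty about the replaced value. The SAP is a methods text, and its silence shows only that no such analysis is described.

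Finally, this is one disclosed score on one of six secondary scales in a 16-patient pilot. That limits the weight of the point, but not the reason for a cheap check.

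**Conclusion.** The point holds as a minor one, limited to CFS. A score was replaced after data collection on a criterion drawn from the outcome itself, with no prior rule and no analysis of the observed score described.

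Its possible effect on the between-arm difference in total change is about 0.11k to 0.13k baseline SD for a baseline or 1-month score, or about two full ROPE widths at k = 3. It is small for a 1-week score. These figures assume eight analysed patients per arm, complete visits, baseline at −1 and an assumed k. Dating baseline at consent lowers the end-visit figures. Because visit, arm, displacement and chosen trend are all unstated, the actual effect cannot be fixed from the documents, and nothing shows that the CFS result is wrong.

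The primary PSFS analysis is not touched. Other secondary outcomes could be affected only through the joint model, and the documents give no basis for putting a size on that.

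**What to change.** Report three CFS analyses with equal prominence: the observed score kept, the score set to missing, and the score replaced as now. The set-to-missing run shows how much the imputation model itself contributes. In each, recompute the baseline SD and ROPE where the score is a baseline one, and repeat both the linear/piecewise selection and the joint model.

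State the visit, the arm, the observed value, the reason for doubting it, whether the judgement was made blind to arm, and the imputation model with the number of imputations. Draw a CFS conclusion only if it holds with the score kept and with it replaced.

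Making the doubted score the main analysis is not required, nor is changing the residual distribution. Those are matters of preference.

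The cost is a few extra model runs on data already in hand and a few lines of text. The CFS interval may widen, and a CFS conclusion that depends on one score would have to be withdrawn.
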